### **Aim 1: Identify and enroll 20 pediatric patients with ASBI and PSH.**

**Methods:** Parent(s)/legal guardians, 18 years or older, will be approached for informed consent if their child has ASBI and is exhibiting clinical signs and symptoms of PSH. Once consented, the CFS scoring tool (Table 1a,) will be used to evaluate patients felt to be exhibiting symptoms of PSH to identify eligible ASBI patients. Patients with CFS score > 6 will be eligible for enrollment in the study.

Families of patients who do not meet the CFS score criteria > 6 will be told their child did not meet scoring criteria of study and will be considered consented but not enrolled in study.

Study Enrollment is defined as meeting CFS criteria of > 6 after consent. If CFS scores are already being collected for subject prior to subject consent as a standard of care, we can use already available CFS scores from medical record. The PENFS device will be placed over the external ear by study investigator or one of trained nurses (RNs) from the Pediatric Translational Research Unit (P-TRU) within 24 hours of meeting CFS > 6 score criteria..

There are 380-400 PICU admissions/year that are seen by ICU Neurology. Using a conservative estimate of 8-10% incidence of PSH, we expect to have 35-40 patients with PSH. At a conservative 60% enrollment rate, we expect to be able to successfully enroll 20 patients in this pilot study. Previous studies using the device has shown it to be well-tolerated with minimal side effects (25,26). In a large, randomized sham-controlled trial Kovacic et al showed a very low rate of discontinuation of the device due to side effects. We hypothesize that the dropout rate will be ≤ 10%. Tolerability of the device will be assessed by subjective assessments of device tolerance by the bedside nurse, the CFS score (increasing score after device placement would suggest worsening PSH symptoms) and skin integrity (bedside nurses will perform routine skin evaluation and care while the device is in place.). To evaluate safety, we will monitor for serious adverse effects such as cardiac dysrhythmia (EKG monitoring), and new-onset seizures.

### **Aim 2a: Evaluate feasibility of scoring PSH symptoms using the PSH scoring tool**

**Methods:** The CFS (Table 1a) will be used to score the severity of PSH using the pediatric adaptation for the appropriate age range (Table 2 – diastolic blood pressure will not be used for scoring). CFS scoring will be performed by the bedside nurse who will be trained in using the scoring tool. PSH severity for the 12-hour period prior to placement of the device will be calculated retrospectively based on the features of CFS. After placement of the device, patients will be scored prospectively every 12 hours while the device is worn. The device will be discontinued after 120 hours of wear (usual duration of wear of a device). Scoring will be continued every 12 hours until 120 hours of device placement and then for another 72 hours (total of 192 hours for complete study duration). Every CFS score will be based on the severity of PSH symptoms in the preceding 12 hours.

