
Aim 1: Demonstrate the feasibility of use of PENFS to treat PSH, and tolerability of the device. Hypothesis: The PENFS device will be well tolerated, defined as < 10% early termination from the study. We will recruit 20 patients with ASBI and PSH who will receive PENFS therapy.
 
Aim 2a: Evaluate the feasibility of capturing pediatric PSH symptoms using the CFS scoring tool. Hypothesis: It is feasible to monitor the severity of PSH using a CFS scoring tool (Table 1a,1b). The scoring tool will be adapted for the appropriate age range of the patient (Table 2). We aim for at least 80% scoring (<math>\geq 8/10</math> scheduled scoring per protocol while the device is worn).
 
Aim 2b: Evaluate the effectiveness of the PENFS device in reducing PSH symptoms using change in CFS score. Hypothesis: A decrease in CFS severity score with use of PENFS will be associated with a lower number and/or doses of maintenance and rescue medications for control of PSH symptoms.
 
Aim 3a: Evaluate the change in autonomic balance with use of PENFS device Hypothesis: Heart Rate Variability (HRV) and pupillometry parameters that correspond to sympathetic and parasympathetic activity will be different after PENFS device placement compared to before, reflecting an increase in parasympathetic tone. All patients will be on routine continuous EKG monitoring in the PICU during the study period of interest. Similarly, pupillometry is routinely performed in patients with ASBI in the PICU.
 
Aim 3b: Evaluate feasibility of measuring PENFS effectiveness in treating PSH by a decrease in medication use. Hypothesis: It would be feasible to use the maintenance and rescue medication dosing and frequency as a marker of severity of PSH. PENFS device use will result in lesser number and/or doses of maintenance and rescue medications for control of PSH symptoms. We will compare the pilot sample to a historical cohort to allow power analysis and sample size calculation for a future larger efficacy trial, recognizing that this pilot study is not powered for efficacy.

D. Background, significance, and rationale (including description of preliminary studies and any results):

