### **Aim 2b: Evaluate the effectiveness of the device in reducing PSH symptoms using the change in CFS score**

**Methods:** We will analyze the within-patient change in the modified CFS score with use of the device (before and after device placement and trend in score over time). No maintenance medications will be allowed

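### Aim 2b reads the before/after CFS change as effectiveness, but entry on CFS > 6 and natural decline can both produce a fall with no device effect

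*Combined protocol and SAP*

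**What the plan says.** The specific aims state Aim 2b as: "Evaluate the effectiveness of the PENFS device in reducing PSH symptoms using change in CFS score". The Aim 2b Methods add: "We will analyze the within-patient change in the modified CFS score with use of the device", taken before and after placement and as a trend, with a further comparison of the on-device and post-removal periods. The only confounder acknowledged there is the start of maintenance medication.

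On selection, the Aim 1 Methods say "Once consented, the CFS scoring tool (Table 1a,) will be used to evaluate patients", with entry at CFS > 6. Where routine scoring is already under way, "we can use already available CFS scores from medical record". Aim 1 and Section 4 B both allow up to 24 hours from meeting the criterion to placement.

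On the scores themselves, the Aim 2a Methods say "PSH severity for the 12-hour period prior to placement of the device will be calculated retrospectively based on the features of CFS", then "After placement of the device, patients will be scored prospectively every 12 hours while the device is worn", and "Every CFS score will be based on the severity of PSH symptoms in the preceding 12 hours". Screening & Consent also describes a 12-hour pre-placement score, collected once the child has qualified. Aim 2a uses the pediatric adaptation in Table 2 without diastolic pressure, whereas Aim 1 cites Table 1a for the qualifying score.

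Section 2 A says that PSH symptoms are worst at first and lessen over time. The study has one arm. The data listed for the historical cohort include medications by 24-hour period but no serial CFS.

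**The concern.** Entry requires a high value on the same scale that is later used to measure change. If the qualifying score is the baseline, or is correlated with it more closely than with the post-placement score, the group mean is expected to fall even if the device does nothing. This is regression to the mean. The natural decline described in Section 2 A pushes the same way. Neither is mentioned in Aim 2b or in the data analysis overview, and no control series of CFS scores exists to subtract them.

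At stake is the reading of one result under an aim labelled effectiveness. A fall at placement could be credited to the device and carried into the case for the larger trial, when some or all of it comes from who was let in and when.

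**Working it through.** **Timing.** A qualifying score can precede placement by 0 to 24 hours, and the pre-device score covers the last 12 of those hours. A qualifying score taken 0 to 12 hours before placement therefore falls in the baseline window, and one taken 12 to 24 hours before does not. Overlap is permitted, not required.

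**Stated figure.** The documents give no expected CFS change, so there is none to reproduce. N = 20 is a convenience sample (Section 6 D).

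**Inputs.** From the documents: threshold > 6, that is 7 or more on an integer scale; range 0 to 18 (six items scored 0 to 3, in Table 1a and in Table 2 without diastolic pressure). Assumed: screened mean 6 to 8, SD 3, correlation r between adjacent 12-hour scores 0.4 to 0.8, no device effect and no trend.

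**Formulas** (normal approximation). Let a = (6.5 − mean)/SD and λ = φ(a)/(1 − Φ(a)). The selected group's qualifying score exceeds the screened mean by SD × λ.

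- Qualifying score is the baseline: fall = (1 − r) × SD × λ.
- Qualifying score one window before the baseline, correlation decaying with time (AR(1)): fall = r(1 − r) × SD × λ.
- Separate later baseline, equal correlation between all scores (exchangeable): fall = (r − r) × SD × λ = 0.

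**Numbers.** Mean 6: a = 0.167, λ = 0.907, SD × λ = 2.72. Mean 8: a = −0.5, λ = 0.509, SD × λ = 1.53.

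| Screened mean | r | Qualifying = baseline | One window earlier, AR(1) |
|---|---|---|---|
| 6 | 0.4 | 0.6 × 2.72 = 1.63 | 0.24 × 2.72 = 0.65 |
| 6 | 0.8 | 0.2 × 2.72 = 0.54 | 0.16 × 2.72 = 0.44 |
| 8 | 0.4 | 0.6 × 1.53 = 0.92 | 0.24 × 1.53 = 0.37 |
| 8 | 0.8 | 0.2 × 1.53 = 0.31 | 0.16 × 1.53 = 0.24 |

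Simulation with scores rounded and limited to 0 to 18 gives 0.32 to 1.66 and 0.24 to 0.65 over the same range.

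**Sensitivity.** With SD 2 the simulated ranges are 0.17 to 1.20 and 0.12 to 0.46; with SD 4 they are 0.47 to 2.10 and 0.37 to 0.80. If screened scores sit well above the threshold (mean 10, SD 2), SD × λ = 0.18 and even r = 0.4 gives only 0.6 × 0.18 = 0.11.

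**Does choosing the later score help?** Hold the gap between the qualifying score and placement fixed, and model each score as a 12-hour mean of a process whose correlation decays exponentially (mean 6, SD 3, r = 0.8). At a 6-hour gap, the 12-hour pre-placement score gives a fall of 0.71, against 0.89 with the qualifying score as the before value. At 12 hours the figures are 0.63 and 1.18. The later score reduces the artefact but does not remove it.

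**Scoring versions.** For a 10-year-old, systolic pressure 135 scores 0 on Table 1a and 2 on Table 2; respiratory rate 24 scores 2 and 0. Table 2 has bands for ages 1–4 and 5–15 only, while enrolment runs to 17.

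**The case against.** The strongest defence is that the plan claims little. It disclaims power for efficacy (Aim 3b), says sham randomization would be preferable, and uses mixed models to describe change, with no test named for the step. Hypothesis 2b concerns an association between score and medication, summarised by a Spearman correlation. The post-removal comparison does not use the baseline. All of this stands and limits the severity. It does not answer the point, because low power concerns precision whereas selection causes bias, and the aim is still worded as effectiveness.

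A second objection is that the size is entirely assumed and can be near zero. That is correct, and the range above shows it.

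A third is that an intermediate pre-placement score can show a larger fall than a qualifying score taken right at placement (0.71 at a 6-hour gap against 0.54 at no gap, r = 0.8, mean 6). This compares children with different gaps. At any one gap, the later score gives the smaller fall.

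Three stronger readings are tempting:

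- A reader might infer that the baseline is undefined. Aim 2a and Screening & Consent both describe a 12-hour pre-placement score. Table 3 marks CFS in the −12 to 0 h column and at 0 h, but with a 12-hour look-back these may be one score. What is missing is a sentence tying that score to Aim 2b.
- A reader might infer that a retrospective before score and prospective after scores are measured differently. Every score looks back 12 hours, and "CFS scoring will be performed by the bedside nurse who will be trained in using the scoring tool", so a difference is not established.
- A reader might infer that the tolerability assessment in Aim 1 or the stopping rule in Section 6 C is compromised. Both also rely on other signs, and the effect on them has not been worked out. Stating which score a rise is measured against would be a clarification only.

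**Conclusion.** The concern holds in a limited form. As written, the plan can credit the device with a CFS fall that comes from selection on CFS > 6, from natural decline, or from both, and it names neither. Under the assumed inputs (mean 6 to 8, SD 3, r 0.4 to 0.8, no device effect), selection accounts for about 0.3 to 1.7 points on an 18-point scale if the qualifying score is the baseline, and about 0.2 to 0.65 points if it is one window earlier under AR(1). It accounts for about 0 if a separate baseline is used and scores are exchangeable, and about 0.1 or less if the screened mean is well above 6 with a small spread. Natural decline would add to any of these and cannot be sized from the documents.

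A reader might infer that the artefact is certain, or that it yields a known false-positive rate. The documents support neither: overlap depends on when each child qualifies, and no test of the step is specified. Severity is minor to moderate.

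**What to change.** 1. Main change: in Aim 2b and the data analysis overview, report the before/after step as descriptive and not as evidence of effectiveness. Name regression to the mean and natural decline beside the existing medication caveat.
2. State that the before value is the 12-hour pre-placement score already described in Aim 2a and Screening & Consent. Do not substitute an earlier qualifying score when a later pre-placement score exists, and record the times of both. This reduces the artefact without removing it, so item 1 is still needed.
3. Reconcile Aim 1 (Table 1a) with Aim 2a (Table 2 adaptation) so that qualifying, before and later scores use one scoring version, and state how ages 16 and 17 are scored, for which Table 2 has no bands.

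The cost is wording and two time fields, with no extra scoring. The downside for the investigators is a less favourable statement about effectiveness.

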### **Aim 2b: Evaluate the effectiveness of the device in reducing PSH symptoms using the change in CFS score**

**Methods:** We will analyze the within-patient change in the modified CFS score with use of the device (before and after device placement and trend in score over time). No maintenance medications will be allowed

## Protocol Summary/Submission Application

during the initial 12 hours of use of the device; however, rescue medications will be allowed during this period. Maintenance medications would be allowed after 12 hours of device use. We will also compare the trend in scores while using the device to the trend once the device is discontinued after 120 hours of use as we will be following the trend in the CFS scores every 12 hours for an additional 72 hours after removal of the device. This will be impactful as the patient will be his/her own control. However, we recognize that this could be confounded by the initiation of maintenance medications.

### **Aim 3a: Evaluate the change in autonomic balance with use of PENFS device**

**Methods:** We will use two separate validated modalities to evaluate the autonomic activity/balance in response to use of the device – HRV and Pupillometry. HRV denotes the beat-to-beat variability in the R-R interval on the EKG. Cardiac pacemaker automaticity is continuously altered and regulated by the autonomic nervous system (ANS). The parasympathetic system regulates HR on a beat-to-beat basis whereas the sympathetic system has slower onset but longer duration of action (16-18). Decreased HRV parameters has been shown to be associated with increased 30-day mortality in critically ill patients (19). Children with PSH were shown to have significant differences in HRV parameters compared to controls (20). We will calculate time-domain (mean heart rate, standard deviation of all average R-R intervals (SDNN), root mean square of the successive differences (RMSSD), physical stress index (PSI), approximate entropy (ApEn); successive R-R interval difference (SRD)) and frequency-domain indices (total power (TP), high frequency (HF), low frequency (LF), normalized HF, normalized LF, and LF/HF ratio) and compare the 12-hour period before and after placement of the PENFS device. Three separate 5-minute segments of continuous EKG tracings at rest (lying in bed) and body temperature 36-37.5C will be identified for both periods for comparison. Similarly, we will compare the pupillometry parameters along with direction of change before and after device placement.

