### Data analysis & interpretation (Overview)

**Missing data:** In general, the assumption of missing at random (MAR) will be assumed. Under this assumption, we will impute or use mixed models. A sensitivity analysis, using clinical and biological expertise will be included. **Exploratory data analysis** will include exploration of distributions and relationships of the variables, using summaries, such as correlation, plots such as Loess smooth plots, and Classification and Regression Trees (CART). To satisfy parametric assumptions, transformation of variables will be used or non-parametric tests when necessary. **Continuous data:** we will use mixed models to describe changes over time, the variance covariance matrix will be chosen to be parsimonious but to fit the data and will likely be an autocorrelation matrix. **Design justification:** Although it would be better as a pilot to randomize patients to a sham and active PENFS, the numbers would be so small (and heterogeneous) that the study would have limited information. The next step would be to evaluate the acceptability of randomization in this group of patients.

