## Protocol Summary/Submission Application

*Hypothesis 1:* The number approached and consented will be tracked. Reactions/ adverse events will be summarized and reasons for early termination, if any, evaluated.

*Hypothesis 2a, 2b:* The scoring tool will be adapted for the appropriate age range of the patient (Table 2). We aim for at least 80% scoring ( $\geq 8/10$  scheduled scoring per protocol while the device is worn). The association of the score and the number of doses of maintenance and rescue medications will be summarized with a spearman correlation and exact 95% Confidence intervals (CI).

*Hypothesis 3a:* HRV and Pupillometry measures will be tracked over time with any loss of data recorded with reasons. Wilcoxon Rank Sum test will be used to compare the mean  $\pm$ SD for the parameters for the 12-hour periods before and after device placement.

*Hypothesis 3b:* The number of doses of maintenance and rescue medications for control of PSH symptoms will be compared to historic data using a t-test or non-parametric Mann Whitney. Further a classification tree will be used to evaluate the effect of demographics, clinical history and use of PENFS.

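### Aim 3a compares absolute heart rate variability indices without accounting for mean heart rate, and its wording of SDNN does not match beat-to-beat variability

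*Combined protocol and SAP*

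**What the plan says.** Section E, Aim 3a Methods, explains that "HRV denotes the beat-to-beat variability in the R-R interval on the EKG". It then lists the indices: "We will calculate time-domain (mean heart rate, standard deviation of all average R-R intervals (SDNN), root mean square of the successive differences (RMSSD" and, after these, PSI, ApEn, SRD, total power, HF, LF, "normalized HF, normalized LF, and LF/HF ratio". On the recordings it says "Three separate 5-minute segments of continuous EKG tracings at rest (lying in bed) and body temperature 36-37.5C will be identified for both periods". Pupillometry is compared before and after placement as a second modality.

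Section C states the Aim 3a hypothesis: HRV and pupillometry parameters will differ after placement, "reflecting an increase in parasympathetic tone".

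The analysis text is short. Under Hypothesis 3a, "HRV and Pupillometry measures will be tracked over time with any loss of data recorded with reasons" and a "Wilcoxon Rank Sum test will be used to compare the mean" and SD of each parameter between the two 12-hour periods. The overview adds, for continuous data generally, that "we will use mixed models to describe changes over time"; it names no heart-rate term. Nowhere is mean heart rate used as a divisor, covariate or matching factor.

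**The concern.** An R-R interval is the reciprocal of heart rate, so the same modulation of rate appears as a larger swing in milliseconds when the heart beats more slowly. Six of the twelve listed HRV indices are on an absolute scale. If heart rate is lower after placement for any reason, these can rise although the modulation has not changed, and the stated hypothesis would read that as parasympathetic gain. The design has no concurrent control and allows rescue drugs in the after-period, so the device is not the only possible cause of slowing.

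The definition of SDNN is a second, smaller problem. An SD of averaged intervals is not the beat-to-beat quantity that the same paragraph says HRV denotes, and an analyst following the text could compute something else.

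At stake is the mechanistic conclusion of the pilot, which may be carried into the rationale for a larger trial.

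**Working it through.** **Inputs.** The indices and segment rules come from Aim 3a Methods, and the test from Hypothesis 3a. The documents give no units, expected heart-rate change, HRV standard deviation or power for HRV, so there is no planned figure to reproduce. Units of ms and ms² follow from computing the indices on R-R intervals. The fall from 140 to 120 bpm is an assumption. In Table 2 it moves a child aged 5-15 from heart-rate score 3 to 2, and a child aged 1-4 from 3 to 1.

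**Step 1: R-R interval.** 60,000/140 = 428.6 ms and 60,000/120 = 500.0 ms; ratio 1.167.

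**Step 2: scaling.** A swing of d bpm appears as about 60,000 × d/HR² ms.
- Relative modulation unchanged (d proportional to HR): amplitude × 140/120 = 1.167; power × 1.167² = 1.361.
- bpm swing unchanged (d fixed): amplitude × (140/120)² = 1.361; power × (140/120)⁴ = 1.853.
- Modulation unchanged in ms: both × 1.

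**Step 3: simulation.** Five-minute beat series with equal modulation at 0.10 and 0.30 Hz (each 2% of the rate at 140 bpm). Entries are the value at 120 bpm divided by the value at 140 bpm.

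| Index | Relative constant | bpm constant | ms constant |
|---|---|---|---|
| SDNN | 1.16 | 1.35 | 0.99 |
| RMSSD | 1.34 | 1.56 | 1.14 |
| LF | 1.35 | 1.84 | 0.99 |
| HF | 1.28 | 1.75 | 0.94 |
| Normalized HF | 0.97 | 0.97 | 0.97 |
| LF/HF | 1.05 | 1.05 | 1.06 |
| SDNN / mean R-R | 0.99 | 1.16 | 0.85 |
| RMSSD / mean R-R | 1.15 | 1.34 | 0.98 |
| LF / mean R-R² | 0.99 | 1.35 | 0.73 |
| HF / mean R-R² | 0.94 | 1.28 | 0.69 |

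RMSSD rises more than the amplitude because beats further apart also differ more. For a sinusoid of frequency f the successive difference has amplitude 2A·sin(π·f·RR). At 0.30 Hz, sin(π × 0.30 × 0.5000)/sin(π × 0.30 × 0.4286) = 1.155, and 1.155 × 1.167 = 1.35, close to the simulated 1.34.

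For falls from 140 to 130 through 140 to 110 bpm, over the first two scenarios, SDNN rises 7% to 61% and RMSSD 15% to 100%.

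**Step 4: what division achieves.** It removes the artefact for SDNN, LF and, roughly, HF when relative modulation is constant. It corrects RMSSD only in part (1.34 to 1.15). It leaves every index raised when the bpm swing is constant, and over-corrects when modulation is constant in ms.

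**Step 5: SDNN read literally.** Take three segments at 125, 130 and 135 bpm. The average R-R values are 480.0, 461.5 and 444.4 ms, and their SD is 17.8 ms. With all three at 130 bpm, the simulated SD of the averages is 0.01 ms. The within-segment SDNN is 9.1 ms in both cases. The literal quantity follows drift between segments.

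**Step 6: would it show?** With n = 20, assumed log-scale SDs of 0.5 to 0.7 between and 0.2 to 0.3 within patients, and no change in modulation, a paired signed-rank test is significant in about 30-62% of simulated trials for a 17% rise and 84-100% for a 36% rise. The planned rank sum test, which ignores pairing, gives about 1-3% and 8-36%. It hides the artefact only through low power; the choice of test is a separate matter.

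**The case against.** The strongest reply is that the plan already holds measures free of this scaling. In normalized HF, normalized LF and LF/HF the scale factor cancels. In the simulation normalized HF falls slightly and LF/HF rises slightly, the opposite of a false vagal gain. Pupillometry does not use R-R intervals at all. A reader might infer that the whole Aim 3a conclusion could come from a slower heart; the documents do not support that. What stands is that these measures have no priority, so six raw absolute indices can be read on equal terms with them.

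On SDNN, a reader might infer that it will be computed from three segment averages and will point the wrong way. No text says so. The index is named, the paragraph defines HRV as beat-to-beat, and the background refers to established measurement standards, so loose drafting is the simpler explanation. The wording still conflicts with its own paragraph.

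A fall in heart rate may itself be autonomic: Aim 3a says that the autonomic nervous system regulates pacemaker activity. Unchanged modulation is therefore not the same as no autonomic change. Segments are also restricted by rest and body temperature in both periods, which limits activity and fever as causes. Section 2 says that symptoms ease over time but gives no time scale, so it does not establish a fall between adjacent 12-hour windows. If a permitted sympatholytic rescue drug slows the heart, that is drug confounding, which dividing by R-R does not resolve. These points limit how likely and how large the artefact is; they do not supply the missing adjustment.

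A reader might also infer that the plan offers HRV as confirmation independent of the CFS, of which heart rate is an item. It does not. It calls HRV and pupillometry two separate modalities, which is a different claim.

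**Conclusion.** The concern holds for SDNN, RMSSD, SRD, TP, HF and LF. With heart rate unaccounted for, a fall from 140 to 120 bpm raises ms amplitudes by about 17% or 36% and power by about 36% or 85%, depending on whether relative modulation or the bpm swing is constant. RMSSD moves further, by about 34% or 56% in simulation. If modulation is constant in ms, SDNN and HF barely change and RMSSD rises about 14%. The size rests on an assumed heart-rate change and on which form of modulation is constant; the documents settle neither. SRD and TP were taken from their definitions and the scaling, not tabulated separately.

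The SDNN wording should be corrected, whatever was intended. The consequence is confined to a mechanistic aim in a convenience-sample pilot of 20 patients; feasibility and tolerability are untouched. The change is worth making because it is cheap and needs no new data.

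**What to change.** 1. Define SDNN as the SD of all normal R-R intervals within each 5-minute segment, averaged over the three segments of the period.
2. Beside the raw values, report as a sensitivity analysis SDNN, RMSSD and SRD divided by the mean R-R of the same segment, and TP, HF and LF divided by its square. State that division corrects RMSSD only partly and does not fully correct any index if the bpm swing is constant.
3. Do not conclude increased parasympathetic tone from raw absolute indices alone. Require the rate-corrected indices and normalized HF to agree, with LF/HF not rising. Agreement of raw and corrected values is not enough: in the constant-bpm case both rise, and only normalized HF (0.97) and LF/HF (1.05) block the false conclusion.

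Cost: a revised definition and a few lines of analysis. Mean heart rate is already among the listed parameters, and there is no added burden on patients. Downside: slowing may itself be vagal, so the correction can remove part of a true effect. That is why both versions are reported.
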